## 5.5 Per Protocol Population (PP)

Per Protocol set will include all participants who satisfactorily complete the study and comply with the requirements of the protocol. It is a subset of the ITT population without any major/Critical protocol deviations impacting the primary endpoint of the study.

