### **4.4 End of Study Definition**

The end of the study is defined as the date of the last visit of the last participant in the study.

A participant is considered to have completed the study if he/she has completed all periods of the study including the last visit.

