### **6.4 Study Intervention Compliance**

Participants will be dosed at the study site, directly from the Investigator or designee. The date and time of start of each infusion, as well as the dose and total volume infused, will be recorded in the source documents.

The prescribed dosage, timing, and mode of administration may not be changed. Any departures from the intended regimen must be recorded in the electronic case report form (eCRF).

Noncompliance is defined as taking less than 80% of study treatment during any evaluation period (visit to visit).

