## 10 PROTOCOL DEVIATIONS

Protocol deviations are the deviations from the procedure outlined in the protocol. All the Protocol Deviations (PDs) will be summarized using the ITT population as obtained from Clinical Trial Management System (CTMS) logs. PDs will be identified and discussed with the Investigator/Sponsor in PD review discussion to categorize them, and to finalize analysis population assignment.

Any PDs will be categorized into critical, major and minor protocol deviations and will be summarized based on severity categories. Critical, Major and Minor protocol deviations having impact on primary analysis will be considered while finalizing the Per Protocol (PP) Analysis population. PDs log will be used for reporting purpose in tables. PDs will be summarized based by type and severity for lead-in period and Treatment period. A by patient listing with the specific details for all protocol deviations will be provided.

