### 15.1 Derivations:(Compliance)

The formula used for calculation Overall Compliance will be as follows:

Overall Compliance (%) = (Total amount (mg) of actual doses received in each period / total amount (mg) of planned doses in each period) \* 100.

Compliance will be calculated separately for Lead-in Period and Treatment period respectively.

---

Document: \\needc-vnasc01\Biosdata\Biosidus\Agalsidase Beta\YZAA1358\Biostatistics\Documentation\SAP

Author: [name]

Version Number: V1.0

Version Date: 08May2025

Template No.: CS\_TP\_BS016 Revision 7

Reference: CS\_WI\_BS005

Effective Date: 01Nov2021

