## 16.2.2 Primary Analysis of Primary Efficacy Variable(s)

The primary analysis of the primary efficacy variable will be performed based on both ITT population and PP populations.

The primary efficacy analysis will aim to demonstrate the equivalence in efficacy based on the mean serum Lyso-Gb3 marker ratio after 26 weeks of treatment, considering Serum level of the marker Lyso-Gb3 after 26 weeks divided by plasma level of the marker Lyso-Gb3 at baseline

The primary objective of this study is to test the hypothesis that:

H0: Ratio of serum level of Lyso-Gb3 marker at week 26 and serum level of the marker LysoGb3 at baseline is less than 80% or greater than 125%. This means that there is a difference between AGA BETA BS (Test) and Fabrazyme® (Reference) after 6 months.

H1: Ratio of serum level of Lyso-Gb3 marker at week 26 and serum level of the marker Lyso-Gb3 at baseline is in between 80% and 125%. This means that there is no difference between AGA BETA BS (Test) and Fabrazyme® (Reference) after 6 months.

Mathematically,

H0:  $(\mu_T / \mu_R) \leq 0.80$  or  $(\mu_T / \mu_R) \geq 1.25$

H1:  $0.80 < (\mu_T / \mu_R) < 1.25$

where  $\mu_T / \mu_R$  represent the ratio of means of plasma level of Lyso-Gb3 marker at week 26 and mean of plasma level of the marker LysoGb3 at baseline indicating a difference between AGA BETA BS (Test) and Fabrazyme® (Reference)

A paired t-test will be fit to the log-transformed mean of Lyso-GB3 Marker Baseline value and Lyso-GB3 Marker after 26 weeks of treatment . Equivalence will be declared if the 95% CI for the postbaseline and baseline ratio of plasma level of the marker LysoGb3 is entirely contained within the prespecified equivalence margin of 80% to 125% for the ITT population.

Mean change from baseline of plasma Lyso-Gb3 after 26 weeks of treatment will be calculated and a 95% CI for the difference will be computed. The mean change from baseline and its CI will be exponentiated to obtain the ratio of the means between after 26 weeks of treatment and baseline and its 95% CI. Equivalence will be determined if the 95%CI for the postbaseline and baseline ratio lies completely within the range 0.80 to 1.25 for the ITT population.

Analysis will be performed based on both ITT population and PP population. Descriptive statistics will be presented for the actual and change from baseline data for phenotype wise (classic Fabry males, later onset Fabry males, and Fabry females) and overall, for ITT and PP population.

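### Per-protocol membership for the Week 26 endpoint depends on completing Week 54, and the SAP's only compliance formula does not match its visit-to-visit definition

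*SAP*

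**What the plan says.** **PP set.** SAP 5.5 opens with "Per Protocol set will include all participants who satisfactorily complete the study and comply with the requirements of the protocol" and continues: "It is a subset of the ITT population without any major/Critical protocol deviations impacting the primary endpoint of the study". Protocol 9.2 has the same completion condition. Protocol 4.4 defines completion: "A participant is considered to have completed the study if he/she has completed all periods of the study including the last visit". In the Schedule of Activities the final visit is Day 379, after 54 weeks. Only one PP set is defined, and it serves both the Week 26 and the Week 54 Lyso-Gb3 analyses (SAP 16.2.2 and 16.3.1).

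**Use of PP.** SAP 16.2.2 states: "The primary analysis of the primary efficacy variable will be performed based on both ITT population and PP populations". The same section ties the declaration of equivalence to the ITT population, and Protocol 9.2 describes the use of PP as exploratory.

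**Deviations.** SAP 10 adds: "Critical, Major and Minor protocol deviations having impact on primary analysis will be considered while finalizing the Per Protocol (PP) Analysis population".

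**Compliance.** Protocol 6.4 reads: "Noncompliance is defined as taking less than 80% of study treatment during any evaluation period (visit to visit"). SAP 15 repeats the visit-to-visit wording. The only derivation, in SAP 15.1, is "Total amount (mg) of actual doses received in each period / total amount (mg) of planned doses in each period", times 100, computed once for the lead-in period and once for the treatment period.

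**The concern.** The primary endpoint is fixed when the Week 26 sample is drawn. Nothing that happens later can change whether that value was obtained under the protocol, yet SAP 5.5 lets later events remove it from PP.

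The removal need not be random. Protocol 6.8.2 and 7.1 allow treatment to be stopped, or the participant withdrawn, when the Investigator reads Lyso-Gb3 changes as lack of efficacy. PP can therefore lose participants because of the very variable it tests, and the likely direction is towards a more favourable ratio. In an equivalence trial PP is read beside ITT because non-adherence can pull ITT towards no difference. A PP set conditioned on events after the endpoint is a weaker check.

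The second issue is separate. The compliance class is defined on one time base and derived on another. There is no per-interval formula and no rule for combining intervals into a single class, so the reported class depends on which paragraph the programmer follows.

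**Working it through.** **1. Infusion count (reproduces the plan's figure).** Infusions are every 14 days from Day 1, with none at the final visit on Day 379. Days 1 + 14k for k = 0 to 26 run from Day 1 to Day 365, which gives 27, as both documents state. Assign each visit's infusion to the interval it opens:

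| Interval | Infusion days | Number |
|---|---|---|
| Baseline to 3-month visit | 1 to 85 | 7 |
| 3-month to 6-month visit | 99 to 169 | 6 |
| 6-month to final visit | 183 to 365 | 14 |

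The Day 183 Lyso-Gb3 sample is taken before that day's infusion, so 7 + 6 = 13 infusions precede it.

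**2. Compliance for one pattern.** Take a participant who misses 5 of the 6 infusions on Days 99 to 169 and receives all the others. Body weight is assumed constant, so the mg ratio equals the infusion ratio.

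- SAP 15.1, whole treatment period: (27 − 5)/27 = 22/27 = 81.5%, above 80%. A sixth missed infusion would give 21/27 = 77.8%.
- Protocol 6.4 and SAP 15, visit to visit: 1/6 = 16.7%, non-compliant.
- First dose to the primary sample: (13 − 5)/13 = 8/13 = 61.5%.

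**3. How many participants PP could lose.** Protocol 9.4 plans 16 evaluable participants and 20% dropout: 16/0.8 = 20, which agrees with the plan. With dropout spread evenly over 54 weeks (an assumption), the number with a Week 26 value is 20 × (1 − 0.20 × 26/54) = 18.07, against 20 × 0.80 = 16 completers. The difference is about 2. It is 0 if all four leave before Week 26 and 4 if all leave after it.

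**4. Could PP and ITT then disagree?** The inputs here are assumed, apart from the 18 and 16 of step 3. Of 18 participants with Week 26 data, 16 complete with geometric mean ratio 1.08, and 2 leave after Week 26 with ratio 1.5.

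- PP as written, n = 16, SD of log ratio 0.25: half-width 2.131 × 0.25/√16 = 0.133; interval 1.08 (0.945 to 1.234), inside 0.80 to 1.25.
- All 18: mean log ratio (16 ln 1.08 + 2 ln 1.5)/18 = 0.1135, ratio 1.12. The upper limit is exp(0.1135 + 2.110 × s/√18), where s is the SD over all 18.

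| SD among completers | Upper limit, all 18 |
|---|---|
| 0.25 | 1.27 to 1.28, outside the margin |
| 0.20 | 1.247, just inside |

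The range at 0.25 reflects how s is formed: as the SD itself (s = 0.250), with the leavers exactly at 1.5 (s = 0.258), or with the leavers also varying (s = 0.265). The 1.247 at 0.20 takes the leavers exactly at 1.5. The other two conventions give 1.237 and 1.250, so that case sits at the margin.

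The documents do not settle which SD applies. SAP 16.1 reports a CV of 17.9%. If that is the CV of the ratio, the log SD is √ln(1 + 0.179²) = 0.178 and the upper limit is 1.22 to 1.24. If it is a per-occasion CV, the SD of the log difference is √2 × 0.178 = 0.251 and the SD 0.25 row applies.

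**The case against.** The strongest reply is that PP does not decide anything. SAP 16.2.2 ties equivalence to ITT, SAP 7.3 uses all data obtained in evaluable participants, and someone who leaves at Week 40 stays in ITT. In the illustration, the interval for all 18 is the ITT result, so at SD 0.25 equivalence would not be declared whatever PP showed. This stands. A reader might infer that valid Week 26 data are discarded from the trial, or that PP could produce a false claim of equivalence; the documents support neither.

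On compliance, a reader might infer that a participant with 5 missed infusions is officially compliant and is therefore kept in PP. That does not follow either. Both documents define the class visit to visit, and SAP 15.1 labels its quantity as overall compliance. Neither document makes the class a condition for PP. Missed infusions are departures to be recorded, and deviations with impact on the primary analysis go to the review described in SAP 10, which could remove the participant. Nor is that participant barely exposed before the primary sample, with 8 of 13 infusions received.

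What remains is narrower. The second sentence of SAP 5.5 limits which deviations count, but it does not lift the completion condition in the first. And no derivation in the SAP implements the visit-to-visit definition.

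**Conclusion.** The point holds in a limited form, on two counts.

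First, the completion condition makes PP for a Week 26 endpoint depend on events up to Week 54. About 2 of 20 participants are affected under evenly spread dropout, with a range of 0 to 4. That matters in a set planned at about 16, but it touches only the supportive analysis. Whether PP and ITT would disagree is not predictable from the documents: it turns on the unstated SD of the log ratio and on how far the leavers' ratios differ. The illustration shows only that disagreement is possible at SD 0.25 and marginal at 0.20.

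Second, the compliance definition and its derivation conflict, and the same participant can be 81.5% or 16.7%. This affects a descriptive output and, at most, informs the deviation review.

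Neither count undermines the ITT decision rule. Both should be settled before database lock.

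**What to change.** 1. Define PP for the Week 26 endpoint as ITT participants with baseline and Week 26 Lyso-Gb3 present and no major or critical deviation affecting the primary endpoint up to the Week 26 sample. Remove the study-completion condition for this set.
2. Define a separate PP for Week 54, where completion to the last visit is a natural requirement.
3. Reconcile SAP 15.1 with SAP 15 and Protocol 6.4: derive the class from mg received over mg planned in each visit interval, non-compliant if any interval is below 80%, as Protocol 6.4 already says. Keep the SAP 15.1 formula as the overall percentage only.
4. Do not turn the 80% class into a new automatic PP exclusion. With six planned infusions, two missed (4/6 = 66.7%) would exclude a participant, a criterion the documents do not contain. Leave missed infusions to the planned deviation review.

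The cost is SAP wording, one additional population flag and a per-interval compliance derivation. No new data are needed.

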# 6 GENERAL CONSIDERATIONS

All descriptive statistics will be presented by study medication.

Categorical data will be described using absolute and relative frequencies (n and %). Percentages will be presented to 1 decimal place. Continuous data will be summarized using the descriptive statistics (n, mean, standard deviation [SD], quartiles (Q1, Q3), minimum, median, and maximum). The precision of the measurement for each continuous variable will be used to determine the number of decimal places to present in tables, figures, and listings, as specified in [APPENDIX 1](#). Minimum and maximum values will be reported with the same precision as the unit of measure. Inferential statistics are described in primary and secondary efficacy sections of this SAP. Relevant raw and derived variables will be listed in by-patient data listings, sorted by study medication and patient number.

---

Document: \\eedc-vnasc01\Biosdata\Biosidus\Agalsidase Beta\YZAA1358\Biostatistics\Documentation\SAP

Author: [name]

Version Number: V1.0

Version Date: 08May2025

Template No.: CS\_TP\_BS016 Revision 7

Reference: CS\_WI\_BS005

Effective Date: 01Nov2021

## 6.1 Reference Start Date and Study Day

Study Day will be calculated from the reference start date and will be used to show start/stop day of assessments and events.

Reference start date is defined as the day of the first dose of study medication i.e. first intravenous (IV) infusion of AGA BETA BS in Treatment period (period 1), (Day 1 is the day of the first dose of study medication: AGA BETA BS) and will appear in every listing where an assessment date or event date appears.

If the date of the event is on or after the reference start date, then:

Study Day = (date of event – reference start date) + 1.

If the date of the event is prior to the reference start date, then:

Study Day = (date of event – reference start date).

In the situation where the event date is partial or missing, study day, and any corresponding durations will appear partial or missing in the listings.

## 6.2 Baseline

Unless otherwise specified, baseline is defined as the last observed value of the parameter of interest prior to the first intake of AGA BETA BS (this includes unscheduled visits). In the case where the date of last non-missing measurement and the reference start date coincide, then collection time, where available, will be compared with the first dose time to determine whether the measurement is pre-baseline or post-baseline. If time is not available or if assessment time coincides with reference start time, the measurement will be considered pre-baseline, but adverse events (AEs), medications commencing on the reference start date will be considered post-baseline.

Any assessment collected prior to intake of AGA BETA BS will be part of Lead-in period.

## 6.3 Derived Timepoints

Not Applicable

## 6.4 Retests, Unscheduled Visits and Early Termination Data

In general, for by visit summaries, data recorded at the nominal visit will be presented. Unscheduled measurements will not be included in by-visit summaries.

---

Document: \\needc-vnasc01\Biosdata\Biosidus\Agalsidase Beta\YZAA1358\Biostatistics\Documentation\SAP

Author: [name]

Version Number: V1.0

Version Date: 08May2025

Template No.: CS\_TP\_BS016 Revision 7

Reference: CS\_WI\_BS005

Effective Date: 01Nov2021

In case of retest (same visit number assigned), the latest available measurement for that visit will be used for by visit summaries but will contribute to the EOS and EOT values.

Listings will include scheduled, unscheduled, retest and early discontinuation data.

All patients who discontinued from treatment and study will be listed and the reasons for discontinuation will be tabulated.

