**Table 2 Schedule of Activities in the Event of Discontinuation**

Procedure	Study Period	Time of Intervention Discontinuation	Early Discontinuation Visit (participant withdrawn)
Full physical examination		•	•
Urine pregnancy test (WOCBP only)		•	•
Laboratory tests  (hematology and biochemistry)			•
12-lead ECG		•	•
Echocardiogram		•	•
Vital signs 		•	•
SF-36		•	•
BPI-short form		•	•
Phone contact – follow-up		• 	
Anti-AGA antibodies		•	•
Lyso-Gb3 (serum)		•	•
IARs and AE assessment		•	•
Concomitant medication review		•	•

Abbreviations: AE=adverse event; anti-AGA=anti-agalsidase; BPI=Brief Pain Inventory; COVID-19=coronavirus disease 2019; ECG=electrocardiogram; HDL=high-density lipoprotein; IARs=infusion-associated reactions; LDL=low-density lipoprotein; Lyso-Gb3=glabotriaosylsphingosine; SF-36=36-Item Short Form Survey; WOCBP=Women of childbearing potential.

1. Laboratory tests include complete hematology, blood urea nitrogen, electrolytes, phosphate, creatinine (with eGFR calculation), cholesterol (total, LDL and HDL), triglycerides, glycemia, bilirubin (total and direct), aspartate and alanine aminotransferases, alkaline phosphatase, total proteins, albumin, gamma glutamyl transferase, first morning urine and urine albumin-creatinine ratio.
2. Vital signs include heart rate, respiratory rate, body temperature, and blood pressure.
3. After intervention discontinuation, instead of following sequential procedures planned in the study, the participant should receive telephone follow-up at same timepoints of all following planned visits to evaluate general health condition.

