## 17.6 Immunogenicity Assessments

Results for Immunogenicity analysis will be presented under SAF population. The following analyses will be performed: Number and frequency of patients with ADA Neutralization Results to AGA BETA BS sampling results by visit

o Negative

o Positive

o Not Done

Descriptive statistics for percentage neutralization will be provided for all available parameters at protocol specified visits using Number of patients available at each assessment visit, Arithmetic Mean, Median, Minimum Maximum, quartiles and Geometric Mean. Summaries for both Actual and change from baseline will be presented. For geometric mean, the mean and the 95% CIs will be calculated on log transformed data, with subsequent antilog transformations applied.

Document: \\needc-vnasc01\Biosdata\Biosidus\Agalsidase Beta\YZAA1358\Biostatistics\Documentation\SAP

Author: [name]

Version Number: V1.0

Version Date: 08May2025

Template No.: CS\_TP\_BS016 Revision 7

Reference: CS\_WI\_BS005

Effective Date: 01Nov2021

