## 17.8 Echocardiogram

Results from the Echocardiogram will be included in the reporting of this study. Results for Echocardiogram will be presented under SAF.

The following Echocardiogram parameters will be reported for this study:

- Thickness of the Left Ventricular Wall
- Left Ventricular Mass index
- Left ventricular ejection fraction
- Overall Evaluation

The following summaries will be provided for Echocardiogram data:

- Actual and change from baseline by visit (for quantitative measurements)
- The count and percentage of patients for overall Echocardiogram interpretation will be provided as follows

Normal

Abnormal, Not Clinically Significant (NCS)

Abnormal, Clinically Significant (CS)

A patient wise listing of Echocardiogram findings will be provided.

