**For outputs, visits will be represented as follows and in that order:**

Long Name (default)
Screening
Week 1
Week 1 (Every 14 days)
Week 99
Week 183
Week 379

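### A positive anti-AGA result first found in a discontinuation sample is assigned to no row of the immunogenicity tables specified in the SAP

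*SAP*

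**What the plan says.** **Collection.** Protocol Table 2 marks "Anti-AGA antibodies" in both of its columns: when study intervention is discontinued, and at the early discontinuation visit of a withdrawn participant. Protocol 8.3.6 also asks for serum at the final visit from participants who discontinued or were withdrawn. Under Protocol 7.1 and the Table 2 footnote, a participant who permanently stops treatment has telephone contact in place of the remaining planned procedures.

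**Tabulation.** Protocol 9.2.5 summarises anti-AGA at baseline and after 14, 26 and 54 weeks. SAP 17.6, on the Safety population, plans "Number and frequency of patients with ADA Neutralization Results to AGA BETA BS sampling results by visit", with categories Negative, Positive and Not Done. It also plans descriptive statistics for percentage neutralisation at the visits the protocol specifies. It has no row for participants positive at any time or newly positive.

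**Handling rules.** SAP 6.4 states: "In general, for by visit summaries, data recorded at the nominal visit will be presented". It continues: "Unscheduled measurements will not be included in by-visit summaries". Early discontinuation data are named once: "Listings will include scheduled, unscheduled, retest and early discontinuation data". Retests "will contribute to the EOS and EOT values", but neither term is defined or attached to any analysis. SAP 6.3 (derived timepoints) and 6.5 (windowing) are both marked not applicable. The Appendix 1 visit list, introduced by "For outputs, visits will be represented as follows and in that order", has no discontinuation, end-of-treatment or end-of-study entry.

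**The concern.** Stopping may be related to the outcome being tabulated. Protocol 2.3.1 says patients with antibodies have a higher risk of infusion-associated reactions. Protocol 2.3.2 lists inhibition of agalsidase by anti-AGA among the factors on which response depends. Protocol 6.5 and 7.1 make life-threatening reactions, and Lyso-Gb3 changes judged to be lack of efficacy, reasons to stop. A participant who becomes positive between visits and then stops may be one whose antibodies matter most, and the stopping sample is normally the last one available.

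Immunogenicity is a named safety endpoint in a single-arm biosimilar switch study of about 20 participants. If a result of this kind reaches no table, the tabulated immunogenicity can look more favourable than the data the protocol asks sites to collect.

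**Working it through.** **Inputs**
- Planned size: 16, raised to 20 for 20% dropout (Protocol 9.4).
- Post-baseline antibody visits: Days 99, 183 and 379 (schedule of activities).
- Infusions: every 14 days.
- Antibody rate: not given in either document. All positive counts below are assumptions.

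**1. The plan's own figure.** 16 / (1 − 0.20) = 20, which reproduces the stated number. Planned dropouts are 20 × 0.20 = 4.

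**2. Spacing of antibody visits.** (99 − 1)/7 = 14 weeks, (183 − 1)/7 = 26 weeks, (379 − 1)/7 = 54 weeks. The gaps are 14, 12 and 28 weeks, against infusions every 2 weeks. A participant who stops is therefore likely to do so between antibody visits.

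**3. Tracing a stopping sample into the tables**

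| Possible route | What the SAP provides |
|---|---|
| Recorded at a nominal visit (6.4) | Not available to a sample taken between visits |
| Mapped to a nominal visit by a window (6.5) | Not applicable |
| Used in a derived timepoint such as last on-treatment value (6.3) | Not applicable |
| Given its own visit row (Appendix 1) | No such entry |
| Used in an EOS or EOT value (6.4) | Undefined, and used in no analysis |
| Counted in an any-time row (17.6) | No such row |

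No route places the sample in a specified table. Telephone follow-up means that no later scheduled sample would normally replace it.

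**4. What is lost.** The participant still appears at baseline, Week 14 and Week 26 where those samples were taken, and antibodies present then are counted. The loss is positivity arising between the last scheduled sample and stopping.

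**5. Size.** One case among 20 treated is 1/20 = 5 percentage points. Intervals are exact (Clopper-Pearson).

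*Two assumed cases, stopping between Weeks 14 and 26, no other positives.* Week 26 shows 0 positive: 0/18 among those tested (20 − 2 = 18), or 0/20 with 2 Not Done. The any-time rate is 2/20 = 10% (95% CI 1.2 to 31.7%).

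*Four planned dropouts, all stopping between visits, no completer positive.* The Week 54 row among those tested is 0/16 = 0% (0 to 20.6%) throughout.

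| Positive first found at stopping | Any-time rate, Safety population (95% CI) |
|---|---|
| 0 | 0/20 = 0% (0 to 16.8%) |
| 1 | 1/20 = 5% (0.1 to 24.9%) |
| 2 | 2/20 = 10% (1.2 to 31.7%) |
| 3 | 3/20 = 15% (3.2 to 37.9%) |
| 4 | 4/20 = 20% (5.7 to 43.7%) |

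**The case against.** The strongest reply is that nothing in the SAP excludes these samples. The sentence "Unscheduled measurements will not be included in by-visit summaries" concerns unscheduled measurements, whereas discontinuation samples have their own columns in Protocol Table 2. The listings sentence is not exclusive, since it also names scheduled data, which plainly appear in tables. A discontinuation visit could be read as protocol-specified under SAP 17.6. SAP 4.3 says all available safety data will be analysed, SAP 7.3 says all data from evaluable patients will be used, and the table shells are not among the documents. The visit list shows little about intent, because it labels day numbers (99, 183, 379) as weeks. All of this stands against a claim of deliberate exclusion. None of it supplies a row or a rule.

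A reader might infer more than the documents support:
- *That the participant is counted in no immunogenicity table.* This is wrong, for the reason in step 4 of the working.
- *That these samples appear only in listings.* This is an inference from silence. No sentence says so.
- *That Week 26 must read 0/18 and hide the gap.* SAP 17.6 has a Not Done category, and Appendix 1 treats the population count as the usual denominator. The row may read 0/20 positive with 2 Not Done, so the missing samples would show but the positive results would not.
- *That laboratory, ECG and echocardiogram summaries have the same defect.* SAP 17.3 also plans incidence of clinically significant abnormal values, and 17.4 and 17.8 plan counts of overall interpretation. None of these is labelled by visit, so the point is not extended to them.
- *That the missing samples already exist.* The early discontinuation visit is held only if possible (Protocol 7.2), and nothing shows that anyone has stopped.

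Two further replies have some weight. With about 20 participants a listing shows each case, and Protocol 7.2 expects withdrawal to be uncommon. Yet Protocol 9.4 budgets 20% dropout, and a listing gives no reported rate. Finally, the final-visit sample in Protocol 8.3.6, if it means Week 54, could bring some participants back into that row. It does not fit the telephone-only follow-up in 7.1.

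**Conclusion.** The point holds as a gap in specification. As written, a positive anti-AGA result first found in a Table 2 discontinuation sample has no row in the tables of SAP 17.6. The effect on the any-time rate is 5 percentage points per case at 20 treated, up to 20 points if all four planned dropouts were affected. These figures assume 20 treated participants, stopping between scheduled antibody visits, and illustrative numbers of positives.

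That the loss is informative is plausible from the protocol's own statements but not demonstrated. The infusion-reaction statement in Protocol 2.3.1 concerns IgG antibodies, Protocol 8.3.6 describes a binding screen with titres, and SAP 17.6 tabulates neutralisation, so the antibody types must be kept apart. A cumulative count is a better summary than by-visit counts alone and is cheap to add. The point does not affect the primary Lyso-Gb3 analysis.

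**What to change.** 1. In SAP 17.6 add two cumulative rows on the Safety population: *positive at any post-baseline sample* and *newly positive after baseline*. Use scheduled, unscheduled, intervention-discontinuation and early-discontinuation samples. Each row should state whether it refers to binding or neutralising antibodies.
2. In SAP 6.4 state that the exclusion of unscheduled measurements applies to by-visit rows only, and either define the EOS and EOT values and say where they are used, or delete them.
3. Reconcile the final-visit serum sample in Protocol 8.3.6 with the telephone-only follow-up in Protocol 7.1.

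The cost is SAP wording, two table rows and one protocol clarification. The rows use samples the protocol already requires, so they need no extra visits or participants. The downside for the sponsor is that the reported antibody incidence may be slightly higher.
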